#### Original Study Day 1:

Original study day 1 is defined as the day of the first emicizumab dose.

For patients who withdrew before week 1 and have neither received emicizumab nor have an entry in the electronic handheld device or site data entry system, original study day 1 is the date of enrollment, defined as week 1 visit, if available, or the date of informed consent.

#### Up-titration Study Day 1:

Emicizumab is administered at a dose of 3 mg/kg/week for 4 weeks when initiating treatment, followed by 1.5 mg/kg/week for the remainder of treatment period. It is possible to increase the dose to 3 mg/kg/week if protocol defined criteria are met. For all patients whose emicizumab dose was up-titrated to 3 mg/kg/week, up-titration study day 1 is defined as the day of the first higher emicizumab dose (based on eCRF). Up-titration study day 1 is defined for up-titrated patients only.

#### Study Day:

Study day (original or up-titration respectively) of an event/assessment is defined as the date of the event/assessment minus the date of Study Day 1 (original or up-titration respectively). If the result is a positive number or zero, add one day. In other words, there is no day zero.

#### Before therapy:

All events/assessments that occur before the original study day 1 are considered to have occurred before therapy and have a negative study day. AEs occurring at the original study

day 1 are assumed to have occurred after therapy started. For handling of laboratory assessment, see definition of baseline.

Baseline:

Baseline assessment is the last valid assessment before or on original study day 1. As defined in the protocol, for all laboratory and immunogenicity assessments at the original study day 1, it is assumed that the assessment was done before the emicizumab intake. Baseline assessments that are measured only once at screening or week 1 and are not affected by treatment should be considered irrespective of the study day (e.g. gender, height, hemophilia history).

For Haem-A-QoL, Heamo-QoL-SF and EQ-5D-5L, the Week 1 questionnaire is considered to be the baseline irrespective of the collection date/time.

Up-titration Baseline:

For patients who are up-titrated, baseline for this period is defined as the last valid assessment done before or on Up-titration study day 1.

Treatment period:

Treatment period is defined as the time between original study day 1 and last emicizumab injection. For a patient who has not withdrawn from/completed treatment, the end of treatment period is actually defined as the date of the clinical cutoff.

Before up-titration:

The period before up-titration starts on the date of the original study day 1 and ends one day before Up-titration study day 1 or, in case of no Up-titration, either the date of study withdrawal or the cut-off date, whichever comes first.

After Up-Titration:

For patients who are up-titrated, the period after up-titration starts on the up-titration study day 1 and ends on the date of study withdrawal or the cut-off date, whichever comes first.

Follow-up:

Follow-up period starts on the day after the end of the treatment period. Follow-up period ends on the day of withdrawal, completion of follow-up, or at the end of the study as defined in the protocol. Only patients who have an assessment during this time period are considered as having entered follow-up.

Observation time:

Observation time is the time between date of enrollment and the day of death or the last actual assessment in the database (=last date known to be alive). At the time of a database cutoff for patients who have not withdrawn from the study, the cutoff date will be used instead of the last assessment date.

Efficacy periods:

The start of the efficacy period for each individual starts on the date of first emicizumab treatment. The end of the efficacy period is defined as the date of the clinical cutoff or the date of withdrawal from/completion of the treatment whichever is earlier.

For patients who withdraw from the study before reaching the Week 1 visit, the duration of efficacy period is set to 1 day, and it starts and ends on the day of enrollment.

For patients whose dose is up-titrated, the efficacy period ends one day prior to the first day on the up-titrated dose (Efficacy period 1).

For patients whose dose is up-titrated, the bleeds occurring during the administration of the up-titrated dose are analyzed separately. The efficacy period on the up-titrated dose starts with the first day on this dose and ends on the day of the clinical cutoff or the date of withdrawal from/completion of treatment (Efficacy period 2).

For statistical evaluations (e.g. descriptive summaries) of post-baseline data summarized by visit, only measurements at scheduled visits are considered. If a measurement is repeated at a scheduled visit (or time point), then only the latest retest result will be used in calculation of the statistical summary. All data – including unscheduled measurements – will be included in the listings.

If a time interval was calculated in minutes, hours or days and needs to be converted into months or years the following conversion factors will be used:

1 year = 365.25 days

1 month = 30.4375 days

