### **3.2 END OF STUDY AND LENGTH OF STUDY**

The approximate length of the entire study from the first patient enrolled to the last patient, last visit (LPLV; see below) is approximately 3 years. For each individual patient, the study is expected to last approximately 2 years (patients will receive 3 mg/kg/week emicizumab for the first 4 weeks followed by 1.5 mg/kg/week emicizumab for the remainder of the 2-year treatment period). *Patients who discontinue emicizumab prior to the completion of the 2-year treatment period will undergo a Safety Follow-up Visit 24 weeks after the patient's last emicizumab dose or at 2 years after emicizumab treatment start, whichever occurs first.*

The end of this study is defined as the date when the last remaining patient has completed the last visit (i.e., LPLV). The study will end when all patients have been treated with emicizumab for 2 years, or earlier, if one of the following is documented:

Withdrawal of consent

OR

Completed the Safety Follow-up Visit 24 weeks after discontinuing emicizumab

OR

Lost to follow-up

OR

Death.

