### **2.4 ANALYSIS TIMING**

The first interim analysis will be performed once approximately 100 patients have received treatment with emicizumab for at least 24 weeks.

A second interim analysis will be performed when approximately 100 patients have received treatment with emicizumab for at least 52 weeks.

The data from these analyses will subsequently be presented to the independent Data Monitoring Committee (iDMC) in order to enable them to effectively monitor the study (see Section 3.3).

Given the hypothesis-generating nature of this study, the Sponsor may choose to conduct up to two additional interim efficacy analyses (i.e., beyond what is specified in Section 6.9.1 of the clinical study protocol [CSP]).

The final analysis will be conducted when all patients have completed 2 years of treatment or have withdrawn, whichever occurs sooner.

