## **4. STATISTICAL METHODS**

No formal statistical hypothesis tests will be performed and all analyses are considered descriptive.

Categorical data will be summarized using frequencies and percentages (including a category for missing, if appropriate). Continuous data will be summarized using descriptive statistics (N, mean, standard deviation, median, lower quartile, upper quartile, minimum and maximum). Other analysis methods will be specified (below) where applicable.

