## **4.3 ANALYSIS OF STUDY CONDUCT**

A clear account of all patients who enrolled in the study and who entered, discontinued, and completed the initial and maintenance phases of the study will be displayed.

The reasons for premature discontinuation from study treatment and the reasons for study withdrawal will be described in listings and summary tables.

In addition, the number of patients who received dose up-titration will also be described.

Enrollment, major protocol deviations and reasons for early discontinuation will be listed and evaluated for their potential effects on the interpretation of study results. The type of

major protocol deviations and the number of patients with at least one major protocol deviation will be summarized in terms of both the safety and ITT populations. Major protocol deviations related to COVID-19 will be summarized and listed.

Patient disposition table describes the flow of patients through the study up to the cutoff. Patients will be tabulated with:

- Number of patients enrolled
- Number of patients who discontinued prematurely prior to Study day 1
- Number of patients with duration of efficacy period <2 years
- Number of patients who completed 24 months in the study (efficacy period)
- Number of patients with at least one dose up-titration (up-titrated population)
- Number of patients who started safety follow-up (for interim analyses only)
- Number of patients who completed safety follow-up
- Number of patients who discontinued treatment
- Number of patients who discontinued from the study
- Number of patients who completed the study

Number of patients included and excluded from each analysis population is listed and summarized. All analysis populations defined for the study are included.

Major protocol deviations are listed and summarized by category and type of deviation.

A listing of investigators is produced with a column indicating the number of patients enrolled. Also enrollment will be summarized by country and investigator number. Observation time, duration of efficacy period and duration of follow-up (as defined in section 4.1) are summarized descriptively (unit weeks) and categorically (cumulative): >0 week, ≥4 weeks, ≥12 weeks, ≥24 weeks, ≥36 weeks, ≥48 weeks, ≥72 weeks, ≥96 weeks.

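### SAP 4.1 extends completers' observation time to the data cutoff and dates Study day 1 so that patients who withdraw undosed before Week 1 cannot appear in their disposition row

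*SAP*

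**What the plan says.** **Observation time.** SAP 4.1 measures it from enrollment to death or the last actual assessment. It then adds that, at a database cutoff, "for patients who have not withdrawn from the study, the cutoff date will be used instead of the last assessment date". Completion is not mentioned. The treatment-period and efficacy-period definitions in the same section name completion alongside withdrawal.

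**Study day 1.** For treated patients, "Original study day 1 is defined as the day of the first emicizumab dose". For patients who withdrew before Week 1 with no dose and no handheld-device or site entry, "original study day 1 is the date of enrollment, defined as week 1 visit, if available, or the date of informed consent". The opening of SAP 4.1 applies its definitions to all outputs unless otherwise specified, and lists patient disposition among them.

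**Where they are used.** SAP 4.3 summarises observation time as 4.1 defines it, in weeks, both continuously and in cumulative categories up to 96 weeks or more. Its disposition table has a row "Number of patients who discontinued prematurely prior to Study day 1" and separate rows for discontinuing from and completing the study. SAP 4.2.2 counts everyone who signed consent as enrolled.

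**The concern.** The SAP treats completing and withdrawing as different outcomes. SAP 2.4 times the final analysis for when "all patients have completed 2 years of treatment or have withdrawn", and the disposition table separates the two. A rule that switches to the cutoff date for everyone not withdrawn therefore takes in completers, who are likely to be most of the study. They would be credited with observation after their last visit, and in a study meant to supply long-term safety data the reported length of observation would be too long.

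The disposition row has a different fault. It looks intended to show enrolled patients who left before treatment, but the fallback date for the main group of such patients is one they cannot have left before. The table would then disagree with the analysis-population summary in the same section.

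**Working it through.** The plan states no expected observation time, so there is no figure to reproduce. The check applies each rule as written.

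**1. Observation time**

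Inputs from Protocol 3.2: about 2 years per patient and about 3 years from first enrollment to last patient last visit. The implied accrual is A = 3 − 2 = 1 year. SAP 4.1 uses 365.25 days per year, so 1 year = 365.25/7 = 52.18 weeks and 2 years = 104.4 weeks.

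Assumptions: uniform entry over A years and a cutoff at last patient last visit, A + 2 years after first entry. A completer who enters at time e then gets A + 2 − e years instead of 2. The excess is A − e, with mean A/2.

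- A = 1: mean 2.5 × 52.18 = 130.4 weeks against 104.4, an excess of 26 weeks (25%). The first patient enrolled gets about 156 weeks.
- A = 0.5: mean 117.4, excess 13 weeks.
- A = 1.5: mean 143.5, excess 39 weeks.
- A = 1.5 with a cutoff 3 months after last patient last visit: mean 156.5, excess 52 weeks.

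Now let a share w withdraw early, all with less than 104.4 weeks. Completers are spread evenly from 104.4 to 104.4 + 52.18A, so the overall median is 104.4 + 52.18A × (0.5 − w)/(1 − w). The documents give no w; 12% is assumed.

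- w = 0.12, A = 1: (0.5 − 0.12)/0.88 = 0.432, and 104.4 + 52.18 × 0.432 = about 127 weeks. If time stopped at completion the median would be 104.4.
- w = 0.12, A = 0.5 and 1.5: about 116 and 138 weeks.
- A = 1, w = 0.05 and 0.20: 104.4 + 52.18 × 0.474 = 129, and 104.4 + 52.18 × 0.375 = 124 weeks.

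If withdrawals average 1 year, the overall mean for A = 1 is 126.5 against 101.7 weeks at w = 0.05, and 114.8 against 93.9 at w = 0.20. That is 24% and 22% too high.

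**2. How far this reaches**

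- Cumulative categories: the earliest in-window completer has (730.5 − 30)/7 = 100.1 weeks, already above the top cut of 96. No completer changes category.
- Annualized bleed rate (SAP 4.6.1.1): uses the efficacy period, which ends at completion.
- Adverse event rates (SAP 4.9.2): patient-years stop at the earlier of end of follow-up and cutoff.
- Planned interims: with 200 patients entering uniformly, 100 reach 24 weeks at 0.5A + 0.46 years and 52 weeks at 0.5A + 1.00 years. For A from 0.5 to 1.5 these fall at 0.7 to 1.2 and 1.2 to 1.7 years, before anyone completes 2 years.

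**3. The disposition row**

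- Dosed patients: Study day 1 is the first dose, and they cannot have discontinued before it.
- Undosed, withdrew before Week 1, no device or site entry, no Week 1 visit: Study day 1 is the consent date. Nobody withdraws before consenting.
- The same group with a Week 1 visit on record: Study day 1 is a visit they attended.
- Other undosed patients, for example with a device entry: the SAP gives no Study day 1, so whether the row counts them is undefined.

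The patients for whom the fallback date was written therefore cannot be counted in the row.

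**The case against.** **The harm is small.** This is largely right. The study is descriptive ("No formal statistical hypothesis tests will be performed and all analyses are considered descriptive"), no primary or secondary endpoint uses observation time, and the efficacy-period duration beside it would still show about 104 weeks for completers. A reader might infer that bleed rates or adverse event rates are distorted too; their own definitions end at completion or end of follow-up, so they are not.

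**The cutoff sentence may be meant for interims only.** Nothing confines it to them. SAP 4.3 describes patient flow up to the cutoff, and no separate rule covers the final analysis.

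**The never-treated count is not lost.** Correct. SAP 4.3 also summarises who is included in and excluded from each population, and ITT minus safety gives the number. SAP 4.9.2 also glosses study day 1 as the start of therapy, which would rescue the row, but that gloss sits in the adverse event rate calculation, while 4.1 governs disposition. It would also be too strong to say the row must always be zero, since some undosed patients have no Study day 1 at all.

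**A reader might infer a third fault, in the follow-up rule.** SAP 4.1 says "Only patients who have an assessment during this time period are considered as having entered follow-up", while Protocol 3.2 says "Patients who discontinue emicizumab prior to the completion of the 2-year treatment period will undergo a Safety Follow-up Visit", so completers seen after their last injection seem to be misclassified. The documents do not support this. Follow-up in SAP 4.1 is simply the time after the last injection, not the protocol's Safety Follow-up Visit, and the row for starting safety follow-up is produced at interims only. The gap between a completer's last injection and final visit is not given. Barring completers would also leave their adverse events in that gap with no study phase under SAP 4.9.2.

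**Conclusion.** Both points hold on the text, with limited reach. Read literally, the observation-time rule overstates the continuous summary at the final analysis, or at a late optional interim. A completer's mean is about 130 weeks instead of 104, and the overall median about 127 instead of 104 under the assumed 12% withdrawal. These sizes rest on uniform entry, a cutoff at last patient last visit and an accrual period inferred from two approximate durations. The direction needs only staggered entry. The disposition row cannot count patients who withdraw undosed before Week 1, and so would conflict with the population summary whenever there are any.

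**What to change.** 1. In SAP 4.1, Observation time, apply the cutoff date only to patients who have neither withdrawn from nor completed the study, in line with the treatment-period and efficacy-period definitions. The up-titration period definitions also omit completion and can be aligned in the same edit.
2. In SAP 4.3, replace the row on discontinuing before Study day 1 with *Number of enrolled patients who never received emicizumab*, which should equal ITT minus safety.

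Leave the follow-up definition as it is. The cost is two wording changes and small programming edits, with no new data. Reported observation time will be shorter.

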## **4.2 ANALYSIS POPULATIONS**

### **4.2.1 Primary Population (Safety Population)**

The primary analysis population is all patients who have received at least one dose of study medication (safety population).

### **4.2.2 Intend-To-Treat Population**

The intent-to-treat (ITT) population includes all enrolled patients (enrolled patients are defined as patient who signed the informed consent).

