##### **4.5.1 Informed Consent Forms and Screening Log**

Written informed consent for participation in the study must be obtained before performing any study-specific screening tests or evaluations. Informed Consent Forms for enrolled patients and for patients who are not subsequently enrolled will be maintained at the study site. For adolescents (i.e., patients who are 12–17 years of age), an Informed Assent Form will be completed instead. Parents or caregivers of adolescents will also complete an Informed Consent Form.

*The enrollment form will be completed after informed consent and/or assent is obtained. All screening evaluations must be completed and reviewed to confirm that patients meet all eligibility criteria before enrollment. The investigator will maintain a screening log to record details of all patients screened and to confirm eligibility or record reasons for screening failure, as applicable.*

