## **4.6 EFFICACY ANALYSIS**

This is a single arm study and, consequently, no formal treatment group comparisons will be conducted.

The efficacy analyses will be based on the ITT population. Efficacy analyses will be restricted to the period before up-titration, if any, except if stated otherwise.

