#### **4.6.1.1 Bleeds**

The primary analysis will be based on treated bleeds (see definition 2.2.2.2). The number of bleeds over time will be estimated using a negative binomial (NB) regression model, which accounts for different follow-up times. The time that each patient stays in the study (efficacy period) will be included as an offset in the model.

An additional model which adjusts for number of bleeds (< 9 or ≥ 9, according to eCRF) in the last 24 weeks prior to study entry will be used to support the primary analysis.

In the rare case that the negative binomial model does not converge or no bleeds were observed for a given endpoint, the primary analysis will be based on “calculated” annualized bleed rate (ABR).

The ABR is calculated using the following formula (called Calculated ABR on all outputs):

$$\frac{\text{Number of bleeds during the efficacy period}}{\text{Number of days during efficacy period}} \times 365.25$$

The efficacy analyses will include the following endpoints defined in section 2.2.2: treated bleeds, all bleeds, treated joint bleeds, treated target joint bleeds and treated spontaneous bleeds. For each endpoint, the model based ABR will be estimated along with its corresponding 95% CI. In addition, the mean, 95% CI based on Exact Poisson, median, IQR, min and max will be provided for the calculated ABR.

A corresponding listing will be provided which will include for each patient the duration of efficacy period, number of bleeds together with calculated ABR for treated bleeds, all bleeds, treated spontaneous bleeds, treated joint bleeds and treated target joint bleeds (based on data before up-titration only). A separate listing will also be provided for the up-titrated population, based on data on or after the up-titration.

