d=day; eCRF=electronic Case Report Form; EQ-5D-5L=EuroQoL Five-Dimension-Five Levels Questionnaire; FVIII=Factor VIII; Haem-A-QoL=Hemophilia Adult Quality of Life Questionnaire; Haemo-QoL-SF=Hemophilia Quality of Life Short Form; HIV=human immunodeficiency virus; HRQoL=Health-Related Quality of Life; m=months (based on calendar months); PD=pharmacodynamic; PK=pharmacokinetic; Wk=week

Notes: the maximum allowable time between Screening and enrollment is 4 weeks; if the elapsed time between Screening and enrollment is more than 4 weeks, Screening must be repeated.

Except for the bleed/medication records, all other patient data will be collected during clinic visits.

- a. Patients who discontinue emicizumab prior to the completion of the 2-year treatment period will undergo a Safety Follow-up Visit 24 weeks after the patient's last emicizumab dose or at 2 years after emicizumab treatment start, whichever occurs first.
- b. Optional visits, as per the investigator's discretion.
- c. **Written informed consent** must be obtained before any study-specific screening tests or evaluations are performed. For adolescents (i.e., patients who are 12–17 years of age), an Informed Assent Form will be completed instead. Parents or caregivers of adolescents will also complete an Informed Consent Form. The enrollment form will be completed after informed consent and/or assent is obtained. All screening evaluations must be completed and reviewed to confirm that patients meet all eligibility criteria before enrollment.

- d. **Medical history and demographics** data will be collected from patient medical records and documented in the eCRF. Medical history includes hemophilia-related history, clinically significant diseases, procedures (including prior surgeries), use of alcohol and drugs of abuse within the past year, and medication allergies. In particular, sites should record whether the patient has any history of prior ITI, anaphylaxis, or known thrombophilia. It should also include all medication taken in the 4 weeks prior to screening (including prescription drugs, over-the-counter drugs, and herbal/homeopathic remedies and therapies). Any hemostatic medications (e.g. bypassing agents) and other medications used to treat or prevent bleeds in the 6-month period prior to starting emicizumab treatment will also be collected. Demographic data will include age, sex, and self-reported race and ethnicity.

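### SAP 4.2.2 equates enrolled with signed consent, against protocol 4.5.1 and SAP Appendix 2; separately, the 1-day rule gives undosed patients full weight in the per-patient bleed summaries

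*SAP*

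**What the plan says.** On who is enrolled, the documents give different answers.

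- SAP 4.2.2: "The intent-to-treat (ITT) population includes all enrolled patients (enrolled patients are defined as patient who signed the informed consent".
- Protocol 4.5.1: "All screening evaluations must be completed and reviewed to confirm that patients meet all eligibility criteria before enrollment". SAP Appendix 2 note c repeats this rule.
- Protocol 4.5.1 also says "Informed Consent Forms for enrolled patients and for patients who are not subsequently enrolled will be maintained at the study site", so some people consent without being enrolled.
- The notes to SAP Appendix 2 add that "the maximum allowable time between Screening and enrollment is 4 weeks".
- SAP 4.1 (Original Study Day 1), for patients who leave before Week 1 with neither a dose nor a diary entry: "original study day 1 is the date of enrollment, defined as week 1 visit, if available, or the date of informed consent".
- Protocol section 6 defines ITT as all enrolled patients and does not mention consent.

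On what follows for efficacy:

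- SAP 4.6: "The efficacy analyses will be based on the ITT population".
- SAP 4.1 (Efficacy periods): "For patients who withdraw from the study before reaching the Week 1 visit, the duration of efficacy period is set to 1 day".
- SAP 4.6.1.1, after the negative binomial model: "In addition, the mean, 95% CI based on Exact Poisson, median, IQR, min and max will be provided for the calculated ABR". Calculated ABR is bleeds divided by days, times 365.25. It becomes the primary analysis of an endpoint if the model does not converge or no bleeds occur.
- SAP 4.6.1.2 counts patients by number of bleeds and by calculated ABR. SAP 4.6.7 reports mean calculated ABR by subgroup. None of these summaries excludes undosed patients.

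**The concern.** There are two separate problems.

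The first is the definition. Under SAP 4.2.2 the group that protocol 4.5.1 describes as consented but not enrolled could not exist. Literally applied, screen failures belong to the efficacy ITT set. SAP 4.1 then leaves their efficacy period open: it starts at the first dose, or is set to 1 day for those who withdraw, and the SAP does not say whether a screen failure is a withdrawal. A programmer would have to guess.

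The second is the 1-day rule, which applies whichever definition is used. The negative binomial model weights records by time through its offset, but the per-patient summaries do not. A 1-day record without a bleed has a calculated ABR of 0 and falls in the lowest bleed and ABR categories, with the same weight as a patient followed for 2 years. Diary training takes place at Week 1 (SAP Appendix 2 note m), so such records will normally show no bleeds. A zero-bleed share meant to describe emicizumab would then include people who never received it, and would lean slightly in the favourable direction.

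**Working it through.** **Inputs**

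- 200 dosed patients: the planned sample size (SAP 2.3), assumed here to be all dosed.
- Zero-bleed share for treated bleeds: 22 of 35 in study BH29884 (protocol 3.3.1). 22/35 = 62.9%, which the protocol rounds to 63%. Applied here: 0.63 × 200 = 126. That study had a 24-week minimum, so carrying 63% to longer follow-up is an assumption.
- Undosed patients with a 1-day period, u: not in the documents. Assumed 5 to 10, each with no bleed.

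The plan has no figure of its own on this point. Its N=200 precision table (SAP 2.3) reproduces with exact Clopper-Pearson limits (for example 5/200 gives 0.82% to 5.74%) and is not in dispute.

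**Zero-bleed share**, (126 + u)/(200 + u)

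- u = 0: 126/200 = 63.0% (exact 95% CI 55.9% to 69.7%)
- u = 5: 131/205 = 63.9%
- u = 10: 136/210 = 64.8%

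For all bleeds, where the same study had 37.1% with none (protocol 1.2.2.3), about 74/200 = 37.0% would become 79/205 = 38.5% or 84/210 = 40.0%.

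**Mean calculated ABR**, no bleeds on the added records: factor 200/(200 + u)

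- u = 5: 200/205 = 0.976, a fall of 2.4%
- u = 10: 200/210 = 0.952, a fall of 4.8%

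**One bleed on a 1-day record** (rare): 1/1 × 365.25 = 365.25. With u = 10 and an assumed dosed mean of 2, the mean becomes (200 × 2 + 365.25)/210 = 3.64. This shift is unfavourable.

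**Negative binomial ABR.** Ten 1-day records add 10/365.25 = 0.027 years, against 400 patient-years for 200 patients over 2 years. A simulation used an intercept model with log-time offset, rate 2.9, dispersion set so that 63% have no bleeds, and 300 datasets. The ABR fell as follows:

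| Follow-up | u = 5 | u = 10 |
|---|---|---|
| half a year | 0.10% | 0.19% |
| 2 years | 0.16% | 0.32% |

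**Attribution.** The u patients are people who withdraw before Week 1. Those whose eligibility was confirmed are enrolled under protocol 4.5.1 too, so they stay in ITT after SAP 4.2.2 is corrected. The shifts above come from the 1-day rule combined with ITT, and cannot be credited to the SAP 4.2.2 sentence alone.

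**The case against.** The choice looks deliberate. SAP version 2.0 moved efficacy to ITT for agreement with the protocol, and the 1-day rule is written out. Protocol 4.5.1 also has the enrollment form filled in once consent is given, which may be where the SAP wording came from. This explains the wording but does not remove the conflict, because the next sentence of protocol 4.5.1 requires eligibility to be confirmed before enrollment. Using ITT is not itself at odds with the protocol; only the meaning given to enrolled is.

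The records will also be visible. SAP 4.3 reports discontinuations before Study Day 1 and the number in each analysis population. The SAP 4.6.1.1 listing shows each patient's duration. The 12- and 24-week interval tables (SAP 4.6.5) and the sensitivity analysis in patients with at least 12 weeks (SAP 4.6.6) drop 1-day records. All of this stands, and it limits the harm. It does not change the main SAP 4.6.1.1 and 4.6.7 summaries. The SAP 4.6.1.2 categories have no alternative version, and the 12-week restriction also removes patients who were dosed.

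Moving the calculated summaries to dosed patients only would have its own cost. Model-based and calculated ABR would have different Ns, and the population of the primary bleed analysis would depend on whether the model converged. That objection is sound, and the fix therefore adds tables and does not replace any.

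**Conclusion.** The definition conflict is plain on the page and should be corrected. The 1-day rule is a separate and smaller weakness that outlasts that correction.

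The size is small: 0.9 to 1.8 points on the treated-bleed zero share, within a confidence interval about 14 points wide, and 2.4% to 4.8% on the mean calculated ABR. These figures rest on an assumed 5 to 10 undosed zero-bleed records, 200 dosed patients and 63% with zero bleeds. The affected summaries are descriptive and serve a secondary objective. The model-based ABR hardly moves, and the safety population contains dosed patients only.

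A reader might infer that every screen failure enters the bleed tables with a 1-day period, which could make the shifts much larger. The documents do not support that: SAP 4.2.2 read literally puts screen failures in ITT, but SAP 4.1 grants the 1-day period to patients who withdraw and does not say that screen failures count. A reader might also take the figures above as the effect of the SAP 4.2.2 sentence; the attribution step shows why they are not.

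**What to change.** 1. In SAP 4.2.2, define enrolled as consented with eligibility confirmed, in line with protocol 4.5.1 and SAP Appendix 2 note c. State that screen failures are reported in disposition only.
2. Keep the ITT tables and the 1-day rule. Add the zero-bleed, bleed-count, ABR-category and calculated-ABR summaries (SAP 4.6.1.1, 4.6.1.2 and 4.6.7) in patients who received at least one dose, and show the N of each set. Model-based and calculated ABR, including the fallback when the model does not converge, are then available on the same stated population.

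The cost is SAP wording, an entry in the SAP history and a few extra tables. The zero-bleed share may read slightly less favourably in dosed patients. The safety, quality-of-life and preference analyses need no change.
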